Session 1 (Baseline, Pre-Fitting). The baseline testing for Session 1 of Study 3 is nearly identical to the procedures in Session 1 of Study 1. See Section 3g. Thus, only the minor differences will be described here. The comprehensive hearing evaluation, completion of the intake form (Appendix), and reorientation that is needed will be completed with the participant's current hearing aids. Their current hearing aids will be maintained and re-verified to ensure an accurate fit to prescriptive targets. The self-report outcome battery on the current hearing aids will be assessed (COSI, SADL, IOI-HA, and the aided portion 1 of the APHAB). Individual RECDs and REURs will be measured for each ear of each participant. The choice in replacement open vs closed domes will be made following routine clinical procedures. The receiver length will be measured and the dome size (open vs closed) will be estimated using manufacturer measurement tools. The replacement hearing aids will be ordered in ROES.

Session 2-The Intervention 'Visit'.

SoC-open and SOC-closed Group Fittings. These groups will receive the SoC, 30-minute face-to-face fitting appointment 4 weeks after Session 1, the average wait time for a fitting appointment. The right and left hearing aids will be programmed separately to the National Acoustics Laboratory Non-Linear 2 (NAL-NL2) prescription. The REAR of the hearing aids will be verified to the 50-, 65-, and 75-dB SPL prescriptive targets generated by the Verifit 2 system using the Speechmap™ stimulus. The criterion for an appropriate fitting would be ± 3 dB between the output and the prescriptive target from 250 Hz to the frequency in which the unaided threshold crossed the 65-dB SPL target. The real ear aided response for an 85 dB SPL input (REAR85) will be measured using an 85-dB SPL swept pure-tone to ensure that the maximum output of the hearing aids does not exceed the predicted uncomfortable loudness levels of the participant (feedback manager deactivated during this measurement only). The programming options will be optimized based on the information obtained on the intake form (Appendix). The participant will be provided with the manufacturer brochure and programming report from the manufacturer software. Consistent with current SoC, no orientation will be provided.

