Study 1 Power Analysis. The primary outcome of interest is based on fitting accuracy of each ear (i.e., deviation of REAR from prescriptive target across frequency). A power analysis for a repeated measure ANOVA with an effect size $\eta^2 = 0.10$, power ($1-\beta$) = 0.80, and $\alpha = 0.05$ requires a sample size of 100 ears (total of 50 participants) over the two groups. A small effect size is expected, as a small effect size was found in the preliminary data ($\eta^2 = 0.10$). Considering 15% attrition, then 8 additional participants will be needed ($N = 58$) resulting in 29 participants per group.

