Study 1 Data Analysis Plan. A generalized linear model will be applied to examine fitting accuracy. This analysis will examine differences (in dB SPL) for in situ REAR (based on testbox fittings) across frequency between the groups relative to the prescription. Because it is expected that differences within the two ears of the same subject will be smaller than differences across subjects, inclusion of both ears in the same analysis may over inflate the statistical power. However, it is also of interest to ensure that all data are considered. Therefore, we propose to complete separate analyses for the left and right ear, even though we expect the pattern of results to be very similar for each ear. These analyses will determine (1) in situ REARs of the testbox fittings matched the prescription within each group, and (2) if there was an effect of fitting accuracy as a function of style. A generalized linear model will be conducted to compare the expected (from prescription) and actual aided SII within and between groups. Finally, separate mixed model repeated measures ANOVA will be applied to examine group differences among the outcome measure subscales (i.e., SADL subscales, IOI-HA items/subscales, and for the APHAB subscales) to examine differences in outcomes between groups and between current hearing aid fittings and the replacement testbox fittings. For the COSI, the percentage of 'better' and 'much better' responses and the average of the final ability will be calculated across goals and compared between groups via a paired-sample t-test. The subjective outcomes of replacement hearing aids (Session 3) from testbox fittings will also be compared to normative data for each group by comparing our mean, standard deviation, and sample size to those same variables from the published outcome respectively via a Welch test. This will inform whether our outcomes for testbox fittings of replacement hearing aids from each group were consistent with the published norms or not. For the IOI-HA, the IOI-HA norms from the VA ROES DALC database that contains over 100,000 IOI-HA records will be used. In the same fashion, we can select IOI-HA norms from ROES by based on degree of hearing loss and hearing aid style. A

logistic regression also will be conducted to examine if the proportion of responses differ between the groups on the specific telephone and exit survey items of interest.

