Study 2 Power Analysis. The sample size for this aim is based on having 12 monaural hearing aid fittings (3 manufacturers of 1 open RIC, 1 closed RIC, 1 open RITA, and 1 closed RITA) per participant (ears counterbalanced across participants such that odd-numbered subjects obtain fittings in the left ear and even numbered in the right ear). To ensure a wide range of RECDs and the expected variability in slit leak venting with closed domes, our target sample size is now 96 participants. See randomization Table in Appendix 6 in the grant application for details. For this single session study, we will account for 10% attrition due screen failure and thus will recruit an additional 10 participants for a total of N = 106.

Study 2 Data Analysis. The data from this study will not be analyzed in the usual manner as the purpose of this study is to develop correction factors for open and closed dome fittings of RIC and RITA style hearing aids from several manufacturers. First the frequency-specific gain deviations for each ear as a function of vent size will be calculated. Second, Linear and nonlinear modeling of these data with the goal of developing a best fit model of the relationship between physical vent size and the frequency specific change in gain. The model will also be adjusted as a function of hearing loss, if necessary, to account for cases when the model correction would erroneously lead to negative gain.

Study 3 Power Analysis. A power analysis based on the same expectations as Study 1 regarding fitting accuracy was conducted. For a mixed model repeated measure ANOVA with an effect size $\eta^2 = 0.10$, power $(1-\beta) = 0.80$, and $\alpha = 0.05$ requires a sample size of 100 ears (total of 50 participants) over the four groups, or 13 participants per group. A small effect size is expected, as a small effect size was found in the SPIRE data ($\eta^2 = 0.10$). Nonetheless, considering increased variability due to venting and to obtain robustness required by clinical standards, we will increase the sample size to achieve higher power of $(1-\beta) = 0.95$. This would bring the sample size of ears to 152, or 76 participants in total (19 per group). Considering 15% attrition, then 12 additional participants will be needed (N = 88) resulting in 22 participants per group.

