Study 3 Data Analysis. We will use a similar data analysis plan as in Study 1 for real ear/fitting accuracy variables. This will determine if derived REARs from open-fit RECD-fittings will accurately meet prescriptive targets and expected aided audibility and if *in situ* REARs of RECD-fittings are equivalent to *in situ* REARs in SoC fittings of open-fit styles. For statistical reasons, we propose to complete separate analyses for the left and right REAR data as described in Experiment 1. For self-report data, a separate mixed model repeated measures ANOVA will be conducted to compare outcomes amongst the groups. This will determine if subjective self-report outcomes across a variety of domains differs as a function of fitting experience and open-fit style.

The data will be analyzed by the PI; her collaborator and co-investigator ([name]., at Vanderbilt University—coded data only) who also will develop the correction factors; and the statistical consultant at Duke University (to be determined). A copy of coded data only will be

stored on the Duke University Server. A copy of all electronic data will also be stored at VA on \\v06.med.va.gov\\dur\\Research\\Research\\[name].

Privacy, Confidentiality, and Information Security

1. Lists of Data Reviewed and/or Collected for Screening/Recruitment and Conduction of Study:

It will be obtained, used, and/or shared for this study includes:

Identifier(s)	Source(s) of Health Information
 Names	 Medical history & physical exam information
 All geographic subdivisions smaller than a State, including street address, city, county, precinct, and zip code. Describe: mailing address	 Photographs, videotapes, audiotapes, or digital or other images
 All elements of dates (except year) for dates directly related to an individual, including birth date, admission date, discharge date, visit or treatment dates, etc.; and all ages over 89, Describe: age, audiology treatment dates (hearing test dates, fitting dates)	 Biologic specimens (e.g., blood, tissue, urine, saliva). Describe:
 Telephone numbers	 Progress notes
 Fax numbers	 Diagnostic / Laboratory test results

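### Study 3 checks each ear's real-ear fit to target on the current aids at Session 1, but the fitting-accuracy model names no baseline covariate, so the experimental versus standard-of-care comparison may be less precise than the data allow

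*Combined protocol and SAP*

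**What the plan says.** The primary outcome is defined under Study 1 Power Analysis as fitting accuracy per ear, the "deviation of REAR from prescriptive target across frequency". Study 3 Power Analysis adopts the same expectations.

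The model is in Study 1 Data Analysis Plan, a generalized linear model run separately for left and right ears: "This analysis will examine differences (in dB SPL) for in situ REAR (based on testbox fittings) across frequency between the groups relative to the prescription". Study 3 Data Analysis carries it over: "We will use a similar data analysis plan as in Study 1 for real ear/fitting accuracy variables". Neither section names a covariate. The only planned comparison of current with replacement aids concerns the self-report scales.

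Under Study Interventions, Study 3, Session 1, the plan says: "Their current hearing aids will be maintained and re-verified to ensure an accurate fit to prescriptive targets". That session is described as nearly the same as Session 1 of Study 1, where the fit of the current aids is checked by real-ear measurement and all testing is done ear by ear. The Risk/Benefit Assessment adds that current aids needing repair or adjustment will receive it.

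**The concern.** The primary outcome has a counterpart in the same ear before the replacement aids are fitted. Replacement aids must be of the same style as the current ones, and people with a significant decline in hearing are excluded (Selection of Subjects). Ear-specific obstacles to reaching target, such as canal acoustics or audiogram shape, could therefore recur at Session 3. If they do, they add between-person variation to the comparison of the experimental (EXP) and standard-of-care (SoC) fittings that a baseline covariate would remove.

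Precision matters here. Because left and right ears are analysed separately, each model has about 76 ears, or 19 against 19 within a coupling type, and Hypothesis 3a asks whether the two approaches are equivalent, a question that interval width bears on directly. The Design section describes random assignment to EXP or SoC, so adjustment would serve precision. Study 1 compares non-randomised style groups, and the covariate would not serve the same purpose there.

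**Working it through.** **Inputs from the documents.** Study 3 Power Analysis: eta² = 0.10, alpha = 0.05; 100 ears for power 0.80; 152 ears (76 participants, 19 in each of four groups) for power 0.95; 15% attrition, giving 88. Study 3 Data Analysis: separate left and right models, so about 76 ears each.

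**Assumed.** rho, the correlation between the Session 1 and Session 3 deviations in the same ear. The documents give no value.

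**Step 1: the plan's own figures.**
- Both ear counts are reproduced by a repeated-measures test of the group-by-frequency interaction with Cohen's f = 0.10, two groups, m = 7 measures and a correlation c = 0.5 among them. These settings are inferred, not stated; they were the only exact match in the grid searched.
- Noncentrality is N × f² × m/(1 − c). N = 100: 100 × 0.01 × 7/0.5 = 14.0, power 0.808. N = 152: 21.28, power 0.953.
- Taken literally, eta² = 0.10 means f² = 0.10/0.90 = 0.111. A one-way test of four groups then needs 103 and 159 ears, and 152 ears give power 0.941.
- Attrition: 76 × 1.15 = 87.4, rounded up to 88.

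**Step 2: effect of a covariate.** Adjustment multiplies residual variance by 1 − rho², so intervals shrink by the factor √(1 − rho²). For one value per ear and a single EXP − SoC contrast with coupling retained (four cells, 1 numerator df, N = 76), noncentrality is 0.111 × 76/(1 − rho²) = 8.444/(1 − rho²). Error df is 72 unadjusted and 71 adjusted.

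| rho | 1 − rho² | noncentrality | power | interval width |
|---|---|---|---|---|
| unadjusted | 1 | 8.44 | 0.82 | 1.00 |
| 0 | 1 | 8.44 | 0.82 | 1.00 |
| 0.2 | 0.96 | 8.80 | 0.83 | 0.98 |
| 0.3 | 0.91 | 9.28 | 0.85 | 0.95 |
| 0.5 | 0.75 | 11.26 | 0.91 | 0.87 |

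A covariate with a separate slope at each of seven frequencies is not a 1-df term. Charging seven df in this simple model (error df 76 − 4 − 7 = 65) still leaves power at 0.82 when rho = 0.

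**Step 3: sensitivity to the test chosen.** All at 76 ears and alpha 0.05:
- Four-group omnibus test (3 df), eta² = 0.10: 0.65 unadjusted; 0.67, 0.70 and 0.79 at rho 0.2, 0.3 and 0.5.
- Within one coupling type, 19 v 19: 0.52 unadjusted; 0.53, 0.55 and 0.64.
- Step 1 interaction settings, two groups: 0.67 unadjusted; 0.69, 0.72 and 0.81.

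In all of them the gain is about 2 points at rho 0.2 and depends entirely on rho.

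**Step 4: form of the covariate.** If the tested effect is group by frequency, as Step 1 suggests, one averaged baseline deviation per ear would not reduce the interaction error. The covariate must be frequency-specific or enter with a covariate-by-frequency term.

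**The case against.** The strongest reply is that the plan is silent, not wrong: a generalized linear model admits covariates, and a similar plan does not exclude one. That stands, and it makes this a suggestion for pre-specification.

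Second, rho may be low. The baseline comes from a different device that has just been brought to target. Replacement aids are then programmed to within 3 dB of target, in situ for SoC and in the testbox for EXP. The outcome is already a deviation from the individual's own target. Open or closed domes are chosen afresh at Session 1, so leakage need not recur. In EXP, part of the Session 3 error comes from the coupler prediction and correction factors, which a check of the old aid cannot contain, so the slope could differ by arm. All of this stands and is why no gain can be promised. The reply is only partial: for EXP the 3 dB criterion is met in the testbox, so in situ deviations at Session 3 are not held to it.

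Third, availability is partly inferred. Input levels of 50, 65 and 75 dB SPL are stated for the replacement fittings but not for the check of the current aids, and the plan does not say whether the as-found or adjusted reading is kept. This narrows the fix to matching levels where recorded.

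A reader might infer that the plan throws away substantial precision at no cost, for instance the 12 to 14 points of power that the 19 v 19 and four-group tests show at rho 0.5. The documents do not support that. They give no basis for rho 0.5 between two devices; the four-group test mixes open with closed coupling; and none of these tests addresses equivalence.

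**Conclusion.** The point holds as a modest one. A per-ear real-ear check against target is made at Session 1, and the Study 3 fitting-accuracy model names no baseline covariate, so the EXP v SoC comparison may be less precise than the collected data allow.

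For the single EXP − SoC contrast the illustrative gain is about 2 points of power at rho 0.2, 3 at 0.3 and 9 at 0.5. This rests on one value per ear, eta² = 0.10 taken literally, 76 evaluable ears, and a rho that the documents do not supply. The figures do not give power for the planned analysis across frequency or for equivalence. At rho near zero the loss is negligible. The mismatch between 152 ears in the sample-size calculation and about 76 in each single-ear model matters more and is a separate issue.

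**What to change.** Before Study 3 outcomes are examined, add to Study 3 Data Analysis:

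- The model for Session 3 in situ REAR minus target includes as a covariate the same ear's Session 1 current-aid REAR minus target, frequency-specific or with a covariate-by-frequency term, and at matching input levels where these were recorded.
- One Session 1 reading is used, taken after any maintenance or adjustment and defined identically in EXP and SoC.
- Coupling (open or closed) stays as a factor, and the adjusted EXP − SoC difference is reported with its 95% interval.
- The correlation was unknown at planning, and no gain in power is claimed.

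Limit this to Study 3. The cost is storing the Session 1 values, a few degrees of freedom and a short paragraph of text; no extra visit or participant is needed. If the correlation proves weak, there is little benefit.

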PROTOCOL TITLE: Efficacy of a Coupler-Based Fitting Approach for Experienced Users Receiving Replacement Hearing Aids

PRINCIPAL INVESTIGATOR: [name], Au.D., Ph.D.

VERSION NUMBER AND DATE: Version 10, June 10, 2022

SPONSOR/FUNDING SOURCE: VA RR&D Merit Review C2777-R

Purpose

The overarching purpose of this project is to develop an accurate coupler-based fitting model for experienced hearing-aid users obtaining replacement hearing aids of any style that will result in positive patient outcomes while mitigating a face-to-face fitting visit.

The proposed project addresses three aims:

Specific Aim 1. Develop vent correction factors for testbox fittings of in-the-ear (ITE) and traditional behind the ear (BTE) with custom earmold hearing aids, which will be used to evaluate the real ear to complete difference (RECD)-fitting approach in a sample of experienced users receiving replacement hearing aids. Hypothesis 1a. RECD coupler-based fittings will accurately meet prescriptive targets and expected aided audibility for ITE and traditional BTE styles. Hypothesis 1b. Subjective outcomes from RECD coupler-based fittings will meet or exceed published norms.

Specific Aim 2. Develop correction factors for RECD coupler-based fittings of hearing aids with non-custom coupling (i.e., mini-BTEs with slim tubing and noncustom open canal coupling—open fits). Hypothesis 2. Correction factors will be developed to account for RECD coupler-based fittings with open canals.

Specific Aim 3. To determine if the open-fit RECD-fitting approach is equivalent to the standard of care (SoC) open-fit fitting approach. Hypothesis 3a. Derived REARs from open-fit RECD-fittings will accurately meet prescriptive targets and expected aided audibility and will be equivalent to in situ REARs in SoC fittings of open-fit styles. Hypothesis 3b. The subjective outcomes will not significantly differ between the experimental RECD-fitting group and the SoC group for open-fit styles.

Background and Significance

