short, the test box reference microphone will be calibrated. The probe tube will be inserted 25-27 mm from the intertragal notch in order to ensure placement within approximately 2-5 mm from the eardrum. The foam insert will be placed in the ear canal and care will be taken not move the probe tube during insertion. The RECD transducer will be coupled to the foam insert and the real-ear response will be obtained. The difference between the HA-1 coupler and real ear response is the measured RECD. Clinical application of the proposed model assumes all necessary pre-fitting procedures (e.g. earmold impression, tubing length, RECD) are completed at this session.

Session 2: The Testbox Fitting 'Visit'. Within five business days of receipt of the replacement hearing aids, the testbox fitting 'visit' will occur. The participants will **not** be present during the fitting. The vent size of each hearing aid will be measured. For both groups, the BTE earmold/ITE hearing aid will be attached to the 0.4cc coupler with putty ensuring that the eartip is flush against the opening of coupler and the vent sealed, as is standard with this procedure. The right and left hearing aids will be programmed separately to the NAL-NL2 prescription generated from the Verifit 2 using the measured RECD from Session 1 of each ear. The derived REAR of the hearing aids will be verified to the 50-, 65-, and 75-dB SPL prescriptive targets generated by the Verifit 2 system using the speechmap stimulus. The criterion for an appropriate fitting would be ± 3 dB between the output and the prescriptive target from 250 Hz to the frequency in which the unaided threshold crossed the 65-dB SPL target. We will then apply the refined vent size correction factor we previously determined. The real ear aided response (REAR85) will be measured using an 85-dB SPL swept pure-tone to ensure that the maximum output of the hearing aids does not exceed the predicted uncomfortable loudness levels of the participant (feedback manager deactivated during this measurement only). The programming options will be optimized based on the information obtained on the intake form (Appendix). After programming and verification, the hearing aids will be mailed to the patient along with the manufacturer brochure and programming report from the manufacturer software. A signature will be required to accept the delivery and the delivery will be tracked.

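### Hypothesis 3a and Study 3's target-match clause name derived REARs, which the testbox fitting itself checks against target, although the adopted Study 1 plan tests in situ REARs

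*Combined protocol and SAP*

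**What the plan says.** Under Purpose, Specific Aim 3, Hypothesis 3a reads: "Derived REARs from open-fit RECD-fittings will accurately meet prescriptive targets and expected aided audibility and will be equivalent to in situ REARs in SoC" fittings. It makes two claims. EXP derived REARs meet target, and EXP derived REARs are equivalent to SoC in situ REARs.

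Study 3 Data Analysis opens: "We will use a similar data analysis plan as in Study 1 for real ear/fitting accuracy variables". The Study 1 Data Analysis Plan works on in situ values. It states "This analysis will examine differences (in dB SPL) for in situ REAR (based on testbox fittings) across frequency between the groups", relative to the prescription, and one of its two stated aims is to establish whether "in situ REARs of the testbox fittings matched the prescription within each group".

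The next sentence of Study 3 Data Analysis returns to derived values for target match: "This will determine if derived REARs from open-fit RECD-fittings will accurately meet prescriptive targets and expected aided audibility". For equivalence it switches again and asks whether in situ "REARs of RECD-fittings are equivalent to" the in situ REARs of the SoC fittings.

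The derived REAR comes from the fitting step. In Study 1, Session 2 (testbox fitting), "The derived REAR of the hearing aids will be verified to the 50-, 65-, and 75-dB SPL prescriptive targets", with a ±3 dB criterion for an appropriate fitting. The vent correction factor is mentioned after that check. Study 3 applies the same procedure to the EXP groups, with correction factors from Study 2, and says the measured RECD will be corrected.

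Study 3, Session 3 measures in situ REARs in every group one month after fitting. It assigns them to comparisons within and between groups, and to judging EXP accuracy relative to SoC.

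**The concern.** Aim 3 asks whether a fitting made in a testbox, without the patient, gives the right output in the patient's ear. The derived REAR is the testbox prediction of that output, and the audiologist adjusts the aid until the prediction is close to target. Finding afterwards that it is close to target mostly shows that the adjustment was done. It does not show that the prediction was right.

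The hypothesis, the adopted plan and the sentence interpreting that plan do not name the same variable, so a conclusion on Hypothesis 3a could be drawn from either one. A favourable target-match statement taken from derived REARs could be read as evidence of real-ear accuracy, which it is not. The equivalence claim has a similar problem: the comparison in the hypothesis is not the comparison in the analysis section.

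**Working it through.** **1. The plan's own figure.** Study 3 Power Analysis uses η² = 0.10 and α = 0.05, and gives 100 ears for power 0.80 and 152 ears (76 participants) for power 0.95. With f = √(0.10/0.90) = 0.333, a one-way F test on four groups and ears treated as independent, power is 0.790 at 100 ears and 0.941 at 152. Both are close to the stated values. For attrition, 76 × 0.15 = 11.4, taken as 12, and 76 + 12 = 88. None of these inputs depends on which REAR is named, so settling this point does not change N.

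**2. The texts side by side.**

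| Place | Against target | Between groups |
|---|---|---|
| Hypothesis 3a | EXP derived | EXP derived v SoC in situ |
| Study 1 plan, adopted by Study 3 | in situ | in situ |
| Study 3 Data Analysis, interpreting sentence | EXP derived | in situ v in situ |
| Study 3, Session 3 procedures | in situ, all groups | in situ, all groups |

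The target-match variable in Hypothesis 3a and the interpreting sentence differs from the one in the adopted plan. For the group comparison, Hypothesis 3a stands alone.

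**3. Why the two variables answer different questions.** For one ear and one frequency, let D = derived REAR minus target, I = in situ REAR minus target, and E = I − D. Then I = D + E. The fitting step acts on D. The accuracy of the RECD method, together with measurement error, lies in E. A test of D contains no information on E.

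**4. Illustration of the gap.** The documents give no SD in dB, so everything here is assumed: D uniform on (−3, 3), E normal with mean b and SD s, one ear, one frequency. The derived share within ±3 dB is then 100% by assumption. At b = 0, with a = 6/s,

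P(|I| ≤ 3) = 2Φ(a) − 1 − 2[φ(0) − φ(a)]/a.

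- s = 2: a = 3, 0.9973 − 0.2630 = 0.734
- s = 3: a = 2, 0.9545 − 0.3450 = 0.610
- s = 5: a = 1.2, 0.7699 − 0.3413 = 0.429

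At b = 3 dB, simulation gives 0.489, 0.458 and 0.371 for the same three SDs. The derived figure is 100% in every case.

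**5. Why a signed mean is not enough on its own.** The Study 1 Power Analysis defines the outcome as "deviation of REAR from prescriptive target across frequency" without saying whether it is signed or absolute; a difference relative to the prescription reads most naturally as signed. If E has mean zero, the mean of I equals the mean of D whatever the SD of E, so comparing signed means does not register ear-to-ear scatter. Using the formula above with both arms at Session 3, an assumed retest SD of 1.5 dB and an added EXP prediction SD of 2, 3 or 4 dB, the EXP SDs are √(1.5² + 2²) = 2.50, 3.35 and 4.27. The shares within ±3 dB are 80% for SoC and 67%, 57% and 48% for EXP, with identical expected signed means. For retest SDs of 1 to 2 dB, the SoC share runs from 87% to 73% and the EXP shares are 63–70%, 54–59% and 47–50%.

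**6. The order of correction and check.** Study 1, Session 2 describes the ±3 dB check and then the correction, with no repeat reading against the three speech-level targets. The Study 3 EXP text says the measured RECD will be corrected, which suggests an earlier point. On the first reading the final derived REAR is not the one checked; on the second it could be. The documents do not settle which applies.

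**The case against.** The strongest reply is that no real-ear test is missing. Study 3 adopts the Study 1 plan, which tests in situ REARs against prescription, and Session 3 collects them in all groups. That stands. A reader might infer that Study 3 never checks the real ear, and the documents do not support that. The defect is in which variable the hypothesis and the interpreting clause name. Nor are derived REARs useless, since the Session 3 text anticipates comparing in situ with derived values in the EXP groups.

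A reader might also infer that SoC values from Session 2, taken just after adjustment to ±3 dB, could be set against EXP values a month old. Study 3, Session 3 answers this: it assigns the group comparison to the Session 3 measurements and gives the SoC repeat the separate task of assessing measurement variability. At most, the analysis section could repeat the session number.

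A third reply is that a match by construction is too strong. This also stands in part. The ±3 dB figure is a criterion, and the text does not say that every ear attains it. If the correction follows the check, the final derived REAR is not guaranteed to match, and testing it would say something. It would still concern the testbox prediction rather than the ear.

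Finally, the scatter point could be pressed into a demand for a different primary model. It does not support that. It supports descriptive summaries beside the planned model.

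**Conclusion.** The point holds on the text. Hypothesis 3a and the Study 3 target-match clause name derived REARs, a quantity the fitting procedure itself checks against target, while the adopted plan tests in situ REARs. The equivalence comparison in Hypothesis 3a also differs from the one in the analysis section. A target-match conclusion drawn as written would largely restate the programming step, with the qualification that the place of the correction is unresolved.

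The effect on the trial's results cannot be computed from the documents. The shares shown rest on assumed SDs, a uniform starting distribution, and a single ear and frequency; they illustrate how far the two variables can part and do not estimate harm. The mismatch needs none of these numbers. It should be corrected before analysis: it affects what Study 3 can claim, but the data to put it right are already planned.

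**What to change.** 1. In Hypothesis 3a and Study 3 Data Analysis, name the Session 3 in situ REARs, in EXP and SoC, as the variable tested against target and between groups. Keep derived REARs as a fitting check and for the in situ v derived comparison described under Session 3.

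2. State that the modelled deviation is signed, by frequency. Beside it, report descriptively for EXP and SoC the per-ear absolute deviation and the proportion of ears within ±3 dB in situ, at each input level measured. Read the EXP proportion against the SoC Session 2 to Session 3 variability.

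3. Reconcile the Study 1 testbox text with the Study 3 EXP text on where the correction enters relative to the ±3 dB check, and say which testbox reading is the derived REAR.

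The cost is wording and a little descriptive analysis. The model and the sample size stay as planned. If the correction turns out to follow the check, a corrected testbox reading must also be saved.
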